### **8.7 Primary Safety Endpoint**

One of the primary safety endpoints is the incidence of adverse events and clinical laboratory abnormalities defined as dose-limiting toxicities (Stage 1).

### **8.8 Secondary Safety Endpoint**

Incidence of adverse events, changes in clinical laboratory tests and vital signs over time (Stage 1 and Stage 2).

### **8.9 Extent of Exposure**

Duration of exposure will be defined as the total number of days a subject is exposed to study drug and will be presented as the total number of days from the first dosing date (Day 1) to the last dosing date (date of last dose minus the date of first dose + 1).

The total cumulative dose will be defined as the sum of the received doses across all study days. The average daily dose and cumulative dose will be summarized by descriptive summary statistics.

A summary of each subject's exposure will be presented in a listing.

### **8.10 Adverse Events**

All Adverse Events (AEs) will be listed as described on the eCRF.

An adverse event will be any untoward medical occurrence in a trial subject who is administered a drug or biologic (medicinal product) or who is using a medical device; the event does not necessarily have a causal relationship with study drug administration or usage.

For this protocol, untoward medical occurrences that should be reported as adverse events will include the following:

- Any unfavorable and unintended symptom, sign (including an abnormal laboratory finding), or disease temporally associated with the use of study drug, whether or not related to the study drug.

- Any pre-existing condition that increases in severity or changes in nature during or as a consequence of study drug administration.
- Any complication that occurs as a result of a protocol-mandated procedure (e.g., venipuncture,) in the screening, study drug administration, or follow-up periods.
- Any injury or accident occurring during the screening, study drug administration, or follow-up periods. If a medical condition is known to have caused the injury or accident (e.g., a fall secondary to dizziness), the medical condition (dizziness) and the accident (fall) should be reported as 2 separate adverse events.
- Any abnormality in physiological testing or a physical examination finding that requires clinical intervention or further investigation (beyond ordering a repeat [confirmatory] test).
- Any laboratory (e.g., clinical chemistry, hematology, urinalysis) or investigational abnormality (e.g., X-ray) independent of the underlying medical condition that requires clinical intervention, results in further investigation (beyond ordering a repeat [confirmatory] test), or leads to investigational medicinal product interruption or discontinuation unless it is associated with an already reported clinical event. If the laboratory abnormality is part of a syndrome, the syndrome or diagnosis (e.g., anemia) not the laboratory result (e.g., decreased hemoglobin) should be recorded.
- A complication related to pregnancy or termination of a pregnancy (see Section 9.7.2 for additional information).

None of the following events will be considered an adverse event:

- Laboratory abnormalities not requiring clinical intervention or further investigation. Such abnormalities will be captured as part of overall laboratory monitoring.
- A diagnostic, medical or surgical procedure (e.g., surgery, endoscopy, tooth extraction, transfusion). However, the medical condition for which the procedure was performed should be reported if it meets the definition of an adverse event. For example, an acute appendicitis that begins during the adverse event reporting period should be reported as the adverse event and the resulting appendectomy should be recorded in the subject's medical records and eCRFs.
- A pre-existing disease or condition or laboratory abnormality present or detected before the initial screening visit and that does not worsen.
- An intervention not associated with an untoward medical occurrence (e.g., hospitalization for elective surgery or for social and/or convenience reasons).
- An overdose without clinical sequela.

Verbatim terms of AEs will be mapped to preferred terms and related system organ classes (SOC) using the Medical Dictionary for Regulatory Activities (MedDRA) Version 16.1. The incidence rate of treatment emergent adverse events (TEAEs), defined as all adverse events reported as new or

worsened after the start of study drug, will be summarized by treatment group, system organ class, preferred term and maximum severity for all adverse events, serious adverse events, adverse events leading to discontinuation of study specified treatment, adverse events leading to discontinuation from the study and fatal adverse events using subjects in the safety population. In addition, summaries of exposure adjusted adverse event rates may also be presented. These summary tables will also be repeated for treatment related adverse events.

Tables will summarize the number and percentage of subjects having an event in each system organ class and preferred term by dose group. The denominator used to calculate incidence percentages consists of subjects receiving at least one dose of RX-0201 in the combination of RX-0201 and Everolimus group.

Further tables will summarize the number and percentage of subjects having adverse events, classified according to severity and the number and percentage of subjects with related events. The order of SOCs presented in tables will be according to the internationally agreed order of SOCs according to MedDRA. Within each SOC, the preferred terms will be shown in alphabetic order.

Note: Subjects who have multiple events in the same SOC and/or preferred term will be counted only once at each level of summation (overall, by SOC, and by preferred term) in the tables. For summaries of AEs by severity, only the highest severity of AE will be counted at each level of summation (overall, by SOC, and by preferred term) in the tables. For summaries of related AEs, subjects with more than one related AE will be counted only once at each level of summation (overall, by SOC, and by preferred term) in the tables.

### **8.11 Death, Serious Adverse Events and other Significant Adverse Events**

A listing of subjects who died on study will be presented.

Tables will summarize the number and percentage of subjects having a serious adverse event in each SOC and preferred term. Further tables will summarize the number and percentage of subjects having serious adverse events judged to be related to RX-0201.

The order of SOCs presented in tables will be according to the internationally agreed order of SOCs according to Medical Dictionary for Regulatory Affairs (MedDRA) version 21.0. Within each SOC, the preferred terms will be shown in alphabetic order.

A listing of subjects reporting serious adverse events will be included.

A listing of subjects and the adverse events leading to study discontinuation will be presented.

Separate listings will be presented for total adverse events, serious adverse events, adverse events related to treatment with RX-0201 and CTCAE Grade 3 and 4 adverse events.

### **8.12 Pregnancies**

Pregnancy Test results will be presented in by-subject listings for further medical review.

### **8.13 Clinical Laboratory Evaluations**

Abnormal laboratory values will be assessed according to NCI CTCAE v4.03 where possible. The criteria for “clinically significant” laboratory abnormalities include a laboratory abnormality that leads to a DLT or a laboratory abnormality that results in any treatment-emergent therapeutic intervention (i.e., concomitant medication or therapy), or any other laboratory abnormality judged by the investigator to be of other particular clinical relevance.

All relevant clinical laboratory tests will be classified as Low, Normal, and High, or Normal/Abnormal according to the normal ranges. This categorical data will be summarized in shift tables comparing the results at each scheduled post-baseline visit with those at the baseline visit.

When there are multiple values within a visit for a particular laboratory variable, the worst value will be taken (worst being the smallest value for criteria below a certain threshold or the largest value for criteria above a certain threshold). If a subject has both a value below the threshold and a value above the threshold, the value furthest from the threshold will be chosen.

Urinalysis data will be presented in subject listings only.

All laboratory (hematology, coagulation, clinical chemistry, and urinalysis) parameters, values, units, normal range, flags collected (normal/abnormal) in the clinical database will be included in by-subject listings for further medical review. Laboratory values with associated CTCAE version 4 grades will have the associated grade displayed.

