4.3 Exclusion Criteria

Disease Related

- Disease-associated symptoms requiring immediate therapy or other interventions
- Known brain metastases or cranial epidural disease unless adequately treated with radiotherapy and/or surgery and stable for at least 3 months before planned first dose of study drug

Laboratory

- Absolute neutrophil count < $1.5 \times 10^9/L$
- Platelet count < $100 \times 10^9/L$
- Hemoglobin < 9 g/dL
- Bilirubin > 1.5 X upper limit of normal (ULN)
- Aspartate aminotransferase (AST) or alanine aminotransferase (ALT) > 2.5 X ULN (OR > 5 X ULN in the presence of known liver metastases)
- Serum creatinine > 1.5 X ULN OR estimated creatinine clearance ≤ 60 ml/min (Cockcroft-Gault)
- Partial thromboplastin time (PTT) > 1.25 X ULN
- Prothrombin time (PT) > 1.25 X ULN OR international normalization ratio (INR) > 1.4

Medications

- Radiation therapy for bone metastasis within 2 weeks, any other external radiation therapy within 4 weeks before planned first dose of study drug. Systemic treatment with radionuclides within 6 weeks before planned first dose of study drug. Subjects with clinically relevant ongoing complications from prior radiation therapy are not eligible
- Prior treatment with everolimus, or any other specific or selective TORC1/PI3K/AKT inhibitor (e.g., temsirolimus)
- Receipt of any type of small molecule kinase inhibitor (including investigational kinase inhibitor) within 2 weeks before planned first dose of study drug
- Receipt of any type of anticancer antibody (including investigational antibody) within 4 weeks before planned first dose of study drug
- Taking strong inducers or inhibitors of CYP450s for subjects receiving everolimus
- Chronic treatment with corticosteroids or other immunosuppressive agents
- Concomitant anticoagulation at therapeutic doses with oral anticoagulants or platelet inhibitors
- Subjects with a known hypersensitivity to everolimus or other rapamycins (sirolimus, temsirolimus) or to its excipients
- Not recovered from toxicities related to any prior treatments, unless adverse events are clinically non-significant and/or stable on supportive therapy

General

- History of any medical, psychiatric, or social (e.g., addictive disorder) conditions, or laboratory abnormality that in the opinion of the investigator, may increase the risks associated with study participation or treatments that may interfere with the conduct of the study or the interpretation of study results

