9.5.2.2 Laboratory Safety Data

All hematology, chemistry, coagulation and urinalysis will be listed by treatment group and subject. Where normal ranges are available, values outside of the range will be flagged. The data will be summarized by treatment group using standard descriptive statistics at each of the scheduled time point in the study. For continuous parameters, a summary of the changes from baseline to each post dose laboratory assessment will also be produced for each treatment group.

Shift analysis for selected laboratory parameters between baseline and both the final visit worst-case on-study value will be summarized according to NCI CTCAE version 4.03 toxicity grades.

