## Safety Analyses

The incidence of subjects with adverse events and clinical laboratory abnormalities, defined as dose limiting toxicities after 1 cycle of therapy, is one of the primary endpoints. The safety of RX-0201 will be evaluated through reporting using the grading system in the CTCAE version 4.03 for adverse events and laboratory abnormalities. This will be used to grade changes in vital signs, and laboratory assessments to include serum chemistry, hematology, coagulation tests and urinalysis. All statistical methods for safety data will be descriptive in nature.

Dose Limiting Toxicities that occur during Cycle 1 will be tabulated by DLT criteria and RX-0201 dose level. Vital signs will be tabulated and presented as raw data and change from baseline at each time point. Laboratory safety data will be tabulated in shift tables based on laboratory-specific normal ranges. Adverse events will be tabulated by body system, intensity and relationship to study drug.

Vital signs, weight, and data will be summarized using appropriate descriptive statistics, by treatment group and time.

All subjects who receive at least 1 dose of RX-0201 will be included in the final summaries and listings of safety data. All safety analyses will be performed by dose level, treatment cycle, and week, where appropriate.

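### SAP 8.13 omits, without declaring it, the protocol's CTCAE-grade laboratory shift to worst and final values; its normal-range shift tables miss further worsening from an abnormal baseline

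*SAP*

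**What the plan says.** Protocol 9.5.2.2 (Laboratory Safety Data) sets out the laboratory shift analysis: "Shift analysis for selected laboratory parameters between baseline and both the final visit worst-case on-study value will be summarized", and the scale is fixed in the same sentence: "will be summarized according to NCI CTCAE version 4.03 toxicity grades". A connecting word is missing, but the sense is a shift from baseline to the final visit and to the worst value on study. The same section plans a continuous summary: "For continuous parameters, a summary of the changes from baseline to each post dose laboratory assessment will also be produced for each treatment group".

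SAP 8.13 (Clinical Laboratory Evaluations) uses another scale: "All relevant clinical laboratory tests will be classified as Low, Normal, and High, or Normal/Abnormal according to the normal ranges". It also uses other time points: "This categorical data will be summarized in shift tables comparing the results at each scheduled post-baseline visit with those at the baseline visit". The overview under the SAP heading Safety Analyses repeats the basis: "Laboratory safety data will be tabulated in shift tables based on laboratory-specific normal ranges". SAP 8.13 still has abnormal values assessed by CTCAE where possible and shows grades in the by-subject listings.

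Protocol 9.5.1 says that changes to the planned analyses will be described in the SAP. SAP section 11 (Summary of Changes to the Protocol) reports none.

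**The concern.** A normal-range shift table has at most three categories. Once a subject is outside the range at baseline, further movement in the same direction produces no shift, whatever its clinical grade. The protocol's table avoids this by using grades and by taking the worst value on study. If the SAP is programmed as written, the report will have no group-level table showing how far laboratory values deteriorated in subjects who began abnormal.

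Change in laboratory tests over time is a secondary endpoint for Stage 1 and Stage 2 (Protocol 9.2.1.2, SAP 8.8). The analytes concerned are relevant to this drug. Protocol 2.3.2 lists thrombocytopenia, neutropenia and decreased hemoglobin among the most common related events in an earlier combination study, and Protocol 2.3.1 reports red-cell, liver and kidney findings in animals.

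**Working it through.** The plan gives no figure to reproduce for this point, so the check sets the sections side by side.

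**1. The two specifications**

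| | Protocol 9.5.2.2 | SAP 8.13 and Safety Analyses overview |
|---|---|---|
| Scale | CTCAE v4.03 grade | Low/Normal/High or Normal/Abnormal |
| Compared with baseline | Final visit and worst value on study | Each scheduled post-baseline visit |
| Meaning of worst | Across the study | Among multiple values within one visit |
| Parameters | Selected, not named | All relevant tests |
| Continuous change from baseline | Planned | Not mentioned for laboratory data |

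No graded shift and no worst-on-study shift appears elsewhere in the SAP.

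**2. Can a subject be abnormal at baseline?** Yes. The limits are in Protocol 4.3, repeated in SAP 5.3.2.

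- Bilirubin is excluding only above 1.5 x ULN, so values from just above ULN to 1.5 x ULN may enter.
- AST and ALT are excluding only above 2.5 x ULN, or 5 x ULN with liver metastases, so values from just above ULN to those limits may enter.
- For these analytes the limits are multiples of ULN, so no normal range has to be assumed: such a subject is High at baseline, and every later rise is High to High.
- Hemoglobin is excluding at "Hemoglobin < 9 g/dL", so 9 g/dL or more may enter. Platelets of 100 x 10^9/L or more may enter. These subjects are Low at baseline only if the local lower limit of normal lies above their value. That is an assumption, since the documents give no normal ranges.

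**3. What the table then misses.** Protocol 6.5 puts Grade 4 thrombocytopenia below 25 x 10^9/L. Suppose a subject enters at 100 x 10^9/L and the local lower limit is higher than that. A fall to just under 25 is a loss of about (100 - 25)/100 = 75%, into Grade 4, and is recorded as Low to Low. The protocol's table would show it as a shift to Grade 4.

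**4. What scheduled visits capture.** In Appendices A and B of the protocol, on-treatment safety laboratory tests fall only around Day 1 of each 21-day cycle, then at end of treatment. Day 1 of a later cycle follows the 7-day RX-0201 rest, and Protocol 6.6.2 has a new cycle wait for laboratory abnormalities to return to baseline. Day 1 values may therefore lean towards recovery. Extra monitoring during toxicity (Protocol 6.6.1) and unscheduled visits (Protocol 7.7) are where a peak or nadir may be found. SAP 7.1 defines no analysis window, so no rule assigns those values to a scheduled visit.

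**5. Other routes for the same information**

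- By-subject listings cover all laboratory values in the database, with grades.
- Under SAP 8.10, an abnormality that needs treatment or work-up, or that leads to interruption or discontinuation of study drug, is an adverse event unless it belongs to one already reported. Treatment-emergent events are tabulated by maximum severity. Abnormalities below that threshold are not adverse events.
- DLTs are tabulated by criterion and dose level, for Cycle 1 only.

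**The case against.** The strongest reply is that little is hidden. A reader might infer that worsening cannot be seen anywhere, or that grades survive only in listings. Neither is supported. About 32 subjects are planned, and the listings show every value with its grade, including values from unscheduled visits if they are in the database. Severe worsening will often need treatment or work-up and so reach the adverse event tables by maximum severity. Several DLT criteria are laboratory grades. What these routes leave untabulated is mainly worsening that does not meet the adverse event or DLT definition.

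Second, a reader might infer that the sponsor withdrew the graded shift. The SAP does not say so. Its statement that nothing has changed could be read as leaving the protocol's analysis in force, and the same applies to the continuous change-from-baseline summary. This stands as far as it goes: the defect is an undeclared omission. But the SAP states the normal-range basis twice, and a programmer working from it would not produce the graded table.

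Third, the protocol limits the shift to selected parameters and names none, so it does not require a table for every gradable analyte, nor does it mention unscheduled values. That is correct. A worst value on study is nevertheless hard to read as excluding values taken between scheduled visits.

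Fourth, the end-of-treatment visit is itself scheduled, so a by-visit table should include it. It would still be on the normal-range scale.

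Finally, creatinine up to 1.5 x ULN might seem to be a further example. The same criterion also excludes an estimated clearance of 60 ml/min or less, which limits who can enter with a raised value, so creatinine is not relied on here.

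**Conclusion.** The point holds as an undeclared omission from the SAP. The protocol's graded shift to the worst and final values is not specified, and the normal-range tables that are specified cannot show further same-direction worsening from an abnormal baseline or extremes found outside scheduled visits. For AST, ALT and bilirubin this follows from the eligibility limits alone. For hemoglobin and platelets it rests on the local lower limit of normal lying above the subject's entry value.

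The size cannot be given as a count, because the documents do not report how many subjects enter abnormal. The loss is a group-level summary for a secondary safety endpoint. The safety analyses are descriptive, dose escalation rests on DLTs and review of safety data, and neither primary endpoint is affected. It should be corrected before database lock, but it does not threaten the trial's main conclusions.

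**What to change.** Add to SAP 8.13 a shift table of baseline CTCAE v4.03 grade by worst post-baseline grade, and by final-visit grade, per treatment group. State that unscheduled values count towards the worst grade. Name the selected gradable parameters, and tabulate each direction separately where an analyte is graded both ways. The protocol does not spell out these details, and the SAP is the place to settle them. Keep Low/Normal/High for ungraded analytes. In the same edit, say whether the protocol's continuous change-from-baseline summary is still planned.

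If the sponsor prefers not to restore the graded table, declare and justify the change in SAP section 11.

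The cost is one extra table set and slightly longer output. Grades are already displayed in the listings, so no new data collection is needed.

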6.5 Definitions of Dose Limiting Toxicity

Reference should be made to the CTCAE, Version 4.03 for grading of the severity of adverse events and laboratory abnormalities. A DLT will be defined as any of the following adverse events that is considered by the investigator as related to RX-0201:

- Grade 4 neutropenia ($ANC < 0.5 \times 10^9/L$) with fever or lasting 3 days or longer
- Any Grade 4 thrombocytopenia or Grade 3 thrombocytopenia associated with \geq Grade 1 hemorrhage
- Any \geq Grade 3 coagulation abnormality (defined by PT and/or INR and PTT values) associated with clinical hemorrhage \geq Grade 1.
- Nausea/vomiting \geq Grade 3 despite maximal antiemetic therapy; diarrhea \geq Grade 3 despite maximal anti-diarrheal therapy.
- Grade 4 thrombocytopenia (platelet count $< 25 \times 10^9/L$)
- Any other non-hematological toxicity \geq Grade 3 with the exception of alopecia

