6.6.1 RX-0201 Dose Modifications During a Cycle

If a subject experiences a RX-0201-related DLT (as defined in Section 6.5), SAE, or other intolerable adverse event and requires a dose reduction, RX-0201 administration should be interrupted, as necessary, until the adverse event resolves or stabilizes to an acceptable degree (generally to the pretreatment severity grade). If appropriate, more frequent laboratory monitoring may be instituted until abnormalities have recovered to the pretreatment severities. Thereafter, RX-0201 may be reinstated, but the dose of RX-0201 for the remainder of that cycle should be reduced by 1 dose level. Successive adjustments to progressively lower dose levels can be made. If the subject cannot tolerate RX-0201 at Dose Level 1 (125 mg/m²/day) then the subject should be discontinued from RX-0201 therapy.

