6.10.10 Erythropoietin and Granulocyte Colony-Stimulating Factors

Use of erythropoietic agents (e.g., erythropoietin or darbepoetin alfa) is not permitted during Cycle 1 in Stage 1. Thereafter, such agents may be administered for Grade \geq 3 anemia, but their use in this study is discouraged.

Granulocyte-macrophage colony-stimulating factor (GM-CSF) should not be administered given the potential for GM-CSF-related inflammatory symptoms.

Use of granulocyte colony-stimulating factor (G-CSF) (e.g., filgrastim, PEG-filgrastim, lenograstim) is not allow during Cycle 1 in Stage 1. Prophylactic administration of G-CSF and concomitant administration of the study treatment(s) and G-CSF is not permitted in support of protocol therapy. However, administration of G-CSF may be considered in a subject who, despite dose modification, is experiencing recurrent difficulties with recovering from neutropenia in a timely fashion. In addition, therapeutic use of G-CSF in subjects with serious neutropenic complications such as tissue infection, sepsis syndrome, fungal infection, etc., may be considered at the investigator's discretion.

Reference may be made to the American Society of Clinical Oncology guidelines (Rizzo et al., 2008; Smith et al., 2006).

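### SAP 8.13 keeps only one result when a visit has both a low and a high value, by an undefined distance, so one abnormality drops out of the laboratory shift table (minor)

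*SAP*

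**What the plan says.** SAP 8.13 sorts results into categories: "All relevant clinical laboratory tests will be classified as Low, Normal, and High, or Normal/Abnormal according to the normal ranges". Shift tables then compare each scheduled post-baseline visit with baseline. The SAP's Safety Analyses text has the same basis: "Laboratory safety data will be tabulated in shift tables based on laboratory-specific normal ranges".

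If a visit holds several values of one variable, the worst is taken, "worst being the smallest value for criteria below a certain threshold or the largest value for criteria above a certain threshold". For the mixed case, where a subject has both "a value below the threshold and a value above the threshold, the value furthest from the threshold will be chosen". Neither sentence identifies the threshold or gives a unit of distance. Urinalysis is only listed, so the rule matters for haematology, chemistry and coagulation.

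Protocol 9.5.2.2 plans something further for selected parameters, a shift from baseline in which the "worst-case on-study value will be summarized according to NCI CTCAE version 4.03 toxicity grades". SAP 8.13 grades abnormal values and shows grades in the listings, but its laboratory text describes no grade-based shift table. SAP section 11 records no changes to the protocol.

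Two protocol provisions bear on how a mixed visit could arise. Under 6.6.1, where appropriate, "more frequent laboratory monitoring may be instituted until abnormalities have recovered to the pretreatment severities". Under 6.10.10, "therapeutic use of G-CSF in subjects with serious neutropenic complications" may be considered, although G-CSF is not allowed in Cycle 1 of Stage 1.

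**The concern.** A result can be abnormal in two directions, and Low/Normal/High classification needs two limits. The rule refers to one unnamed threshold and an unnamed distance. Two programmers could therefore fill different cells from the same data, and whichever reading they choose, one real abnormality disappears from the summary.

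The choice is also not tied to severity. A value's distance from a limit is not its clinical grade, and for an analyte that cannot fall below zero the low side has a ceiling on distance that the high side lacks. Change in laboratory tests is a named secondary endpoint in both stages, and neutropenia and thrombocytopenia are among the toxicities the trial set out to watch.

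**Working it through.** The plan states no figure for this rule, so there is nothing to reproduce. The check is a direct distance calculation.

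**Inputs.** Protocol 6.5 puts Grade 4 neutropenia below 0.5 and Grade 4 thrombocytopenia below 25 (×10⁹/L). I use 0.4 and 20. The documents give no normal ranges, so all ranges below are assumptions, as are the sodium and haemoglobin values. Write L and U for the lower and upper limits, x for the low value and H for the high value.

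**Raw-unit reading, each value against its own limit.** The high value is kept when H − U > L − x, so the break-even is H = U + (L − x). Since x cannot be below 0, any H above U + L wins whatever the low value is.

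| Assumed range | x | L − x | Break-even H | H ÷ U |
|---|---|---|---|---|
| ANC 1.5–7.0 | 0.4 | 1.1 | 8.1 | 1.157 |
| ANC 1.8–7.5 | 0.4 | 1.4 | 8.9 | 1.187 |
| ANC 2.0–8.0 | 0.4 | 1.6 | 9.6 | 1.200 |
| Platelets 130–400 | 20 | 110 | 510 | 1.275 |
| Platelets 150–400 | 20 | 130 | 530 | 1.325 |
| Platelets 150–450 | 20 | 130 | 580 | 1.289 |

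So a neutrophil count up to about 20% above the upper limit, or a platelet count about 30% above it, is enough to displace a Grade 4 low value. Two single cases:
- ANC range 1.5–8.0: 1.5 − 0.4 = 1.1 against 9.2 − 8.0 = 1.2, so High.
- Platelet range 150–400: 150 − 20 = 130 against 540 − 400 = 140, so High.

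**Other scales.**
- Percent of limit: the break-even is U × (1 + (L − x)/L). This gives 12.1 to 14.4 for ANC 0.4 and 738 to 840 for platelets 20.
- Fold: the break-even is U × L/x. This gives 26 to 40 for ANC and 2600 to 3375 for platelets.
- The same pair can change category. With ANC 0.4 and 9.5 and range 1.8–7.5, raw distances are 1.4 and 2.0 (High), percent distances 78% and 27% (Low), and folds 4.5 and 1.27 (Low).

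**A single limit.** If the threshold is read as L alone, a high value is at least U − L away and a low one at most L. In the ranges above, U − L is 5.5 to 6.0 for ANC against L of 1.5 to 2.0, and 250 to 300 for platelets against 130 to 150. Every high value would then beat every low one.

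**Analytes where the high value goes.** Raw units again:
- Sodium 120 and 150, range 135–145: 15 against 5, so Low.
- Haemoglobin 7 and 17, range 12–16: 5 against 1, so Low.

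For sodium the guaranteed-win point U + L is 280, which has no practical force. The direction of loss therefore depends on the analyte and the values; the loss of one direction does not.

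**How often.** Protocol Appendices A and B schedule post-screening haematology, chemistry and coagulation only on Day 1 of each cycle and at end of treatment or early termination. A mixed visit needs repeats assigned to one of these. The documents give no basis for a rate.

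**The case against.** A reader might infer that the SAP has a built-in bias towards High that understates toxicity. The documents do not support that, for five reasons:
- Raw units are not in the SAP. They are the most literal reading, but on percent or fold scales the ANC example stays Low.
- Even in raw units the lean is not general, as sodium and haemoglobin show.
- The trigger is narrow. The rule covers values within one visit, extra monitoring under Protocol 6.6.1 is optional, and unscheduled visits are documented separately (Protocol 7.7). G-CSF rebound cannot affect Stage 1 Cycle 1, which is where DLTs are evaluated.
- DLTs are flagged in the adverse event dataset (SAP 4.3) and tabulated by criterion and dose. An abnormality needing intervention is reportable as an adverse event, and the listings keep every value with its grade.
- The shift table has no grades: an ANC of 1.4 and one of 0.4 fall in the same Low cell. It was never the display for Grade 4 events.

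All of this stands and sets the weight of the point. It does not remove the point. The scale remains undefined, and one direction is still lost. SAP 7.1 defines no analysis window, so nothing settles which repeats belong to a scheduled visit. A laboratory abnormality needing no intervention or further investigation is not an adverse event, and Grade 4 neutropenia without fever lasting under 3 days is not a DLT. For such a value, the laboratory tables are the only summary record. The planned grade-based shift that would recover it is not described in the SAP's laboratory text.

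**Conclusion.** The point holds as a minor one about the summary shift tables. SAP 8.13 discards one abnormality whenever a visit has results on both sides, and it does not define the limit or the scale that decides which. That much rests on the text alone. That a severe neutrophil or platelet count can be tabulated as High rests on the raw-unit reading and on assumed ranges. For other analytes the high result may be the one lost.

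The number of affected visits cannot be estimated and is likely to be very small. The cells are small too: with up to 20 subjects in the combination arm, one subject is 1/20 = 5 percentage points. No conclusion about dose, DLTs or adverse events depends on the rule.

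**What to change.** Replace the mixed-value sentence in SAP 8.13 with: *For parameters with abnormalities in both directions, the lowest value in the visit is used for the shift to Low and the highest value for the shift to High; a subject may be counted in both.* Add a footnote to the table saying so. No threshold or distance scale is then needed.

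Also write into SAP 8.13 the worst-case on-study CTCAE-grade shift for selected parameters that Protocol 9.5.2.2 already plans, by direction.

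The cost is one sentence, a footnote, a second panel for two-sided analytes, and programming a table the protocol already calls for. The downside is that a subject can appear in both panels, so the panels must not be added together. Specifying a scale, or ranking by grade, would also end the ambiguity, but either would still drop one direction.
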